Previous research has examined couples' therapy based treatment for domestic violence across several studies. In these studies, researchers have conducted couple's therapy when working with couples experiencing domestic violence and reported differing, but promising results. In 1984, Taylor used Cognitive Behavioral Therapy in an 8 stage couple's treatment program and, after a 6 month follow up, 65% of the 50 couples treated were "violence-free". In 1985, Riza, Stacey, and Shupe conducted couples therapy, and one year after counseling, 78% reported a reduction or cessation of violence with 79% remaining together. In 2002, Stith, McCollum, Rosen, and Locke conducted couple's therapy with 20 couples with a 43% recidivism rate, and a follow up at 6 months measured by the woman's report of any violence. In 2006, LaTaillade, Epstein, Werlinich implemented the Couples Abuse Prevention Program (CAPP) based on cognitive behavioral couple treatment with 17 couples. They found significant decline in partner hostile withdrawal (withholding emotional contact in a hostile fashion) for men and women, trends toward less humiliating behaviors by their partner in men and women, and a significant decrease in negative communication by males and females. In 2012, Gottman and Bradley implemented the Creating Healthy Relationships Program (CHRP), which is a conjoint couple and relationship education program designed to reduce IPV in low income situationally violent couples. In this study, Gottman and Bradley conducted therapy with 115 couples. Results showed that participation in CHRP prompted an increase in attitudes that reflected healthy relationship skills, predicting a reduction in IPV for the follow up.

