The participants that are assigned to Group 2 will have one additional assessment session at baseline. In order to help those in Group 2 who will not be receiving therapy for the first 8 weeks, individuals in this group will be taught safety planning, given information on local resources to help victims of violence, and will be instructed in stress and anger management strategies. Following this 8 week waiting period, they will receive 8 weeks of couple therapy unless they choose not to. All the physiological and behavioral data collection will be repeated once Group 2 starts therapy.

If a couple discontinues after the baseline and before the end of the study (EOS), the EOS assessments should be obtained.

For couples in Group 1, involvement in the study will last throughout a period of five months with approximately 14 hours of active participation. For couples in Group 2, involvement in the study will last throughout a period of seven months with approximately 16 hours of active participation.

Couple Therapy

Each couple will receive couples therapy for 8 weekly sessions. Each therapy session will last approximately an hour. The therapy sessions will take place in UH Mood Disorders Program, room #12-126, on the 12th floor of the W.O. Walker Center. An attachment and affect regulation based therapy approach will be used in couple therapy.

Principal Investigator: [name]

Protocol Summary for IRB: Feasibility Study of Couple Therapy Treatment for Situational Couple Violence (IRB# 09-13-27)

The participants will receive standard couples therapy that they would have access to outside of the study. The therapy itself is not experimental, but rather it is the data collection, physical measures, and timing which are the experimental portions of the study.

All therapies will be conducted by the PI, [name]. [name] is a Licensed Marriage and Family Therapist and AAMFT (American Association of Marriage and Family Therapy) approved clinical supervisor.

Hypotheses

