All participants in therapy appear more flexible in their relationship positions to one another. Responses are empathetic and emotionally receptive. Both partners monitor and regulate negative affect in an emotionally engaged manner. A sense of connectedness exists between both partners, as well as a decrease in negative cycles.

Principal Investigator: [name]

Protocol Summary for IRB: Feasibility Study of Couple Therapy Treatment for Situational Couple Violence (IRB# 09-13-27)

Data Collection

For each couple, data will be collected at each visit. Data will be collected in two forms:

1. Self-report and partner-report questionnaires will be collected using several measures, all of which have adequate reliability and validity.
2. Physiological data will be collected by monitoring heart rate variability and cortisol level at the DCRU.

Screening Measures

In order to examine eligibility, demographics and some clinical data will be collected.

- CAGE questionnaire. CAGE is a brief alcoholism screening test (Mayfield D, McLeod G, Hall P.1974)
- Simple Screening Instrument for Substance (SSI-SA). Abuse (SSI-SA) The SSI-SA was intended as a brief screen of substance abuse symptoms. It was designed utilizing a binary (yes/no) response format to facilitate scoring and to minimize subjective interpretation of scores Center for Substance Abuse Treatment. (1994).
- Conflict Tactics Scale 2 (CTS2;Straus, Hamby, BoneyMcCoy, & Sugarman, 1996) assesses intimate partner violence based on partners' rating of their own and their spouse's conflict strategies, measuring the intensity and frequency of psychological/verbal and physical conflict. This scale has been shown to have good reliability and validity (Straus, Hamby, BoneyMcCoy, & Sugarman, 1996). This is also be used throughout the study to monitor couple's relationship change.
- Symptom Checklist (SCL90-R) (Derogatis, 1994) will be used to assess acute psychopathology. This measure will also be used throughout the study to monitor participants' mental health change.

Outcome Measures

Both behavioral and physiological measurements will be used to evaluate the effectiveness of conjoint therapy. No medical records will be reviewed at any time.

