Physiological Measures: The change in emotion regulation of participants will be assessed by monitoring the HPA axis and PNS activity. The HPA axis is a major part of the endocrine system that controls reactions to stress. PNS is responsible for simulating the activities when the body is at rest. Therefore, monitoring the HPA axis and PNS activity together will enable assessment of emotion regulation (Porges, 2001). The HPA axis will be monitored using cortisol reactivity, which measures short term changes in the concentration of cortisol, a steroid hormone that is released in response to stress (Böhnke, Bertsch, Kruk, & Naumann, 2010). PNS activity will be monitored accessing vagal regulation (tone, reactivity); that is, the effects produced on the heart when only the parasympathetic nerve fibers are controlling the heart rate. Part of vagal regulation is heart rate variability monitoring, which will be done via eMotion HRV sensor (Please see attached information about the HRV sensor).

Couples will be separated upon arrival and will wait for 15 minutes to reach their resting period, in order for cortisol levels and heart rate to establish a more accurate baseline. The participants will relax by reading previously selected magazines or listening to calming music. They will be

Principal Investigator: [name]

Protocol Summary for IRB: Feasibility Study of Couple Therapy Treatment for Situational Couple Violence (IRB# 09-13-27)

measured for baseline levels of cortisol (via saliva samples) and heart rate variability (via eMotion HRV sensor). The participants will then wait for another 15 minutes.

Then, the couple will be reunited and cortisol and vagal reactivity of both partners will be measured following a discussion of a relationship conflict, in line with the Rapid Marital Interaction Coding System (RMICS) (Heyman & Vivian, 1993). Heart rate will be measured throughout this process. Saliva samples will be collected 15, 30, and 45 minutes following the task.

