Behavioral Measures: At each visit, participants will complete questionnaires measuring attachment patterns, affect regulation, dyadic adjustment, emotional abuse, and IPV. Both partners will fill out the questionnaires separately, in different rooms. The participants will fill out the questionnaires after the collection of physiological data.

Principal Investigator: [name]

Protocol Summary for IRB: Feasibility Study of Couple Therapy Treatment for Situational Couple Violence (IRB# 09-13-27)

Questionnaires include various measures about intimate relationships, all of which have been widely used in previous studies. These measures were chosen based on their conceptual and psychometric qualities. Statistical procedures (e.g., confirmatory factor analyses) will aid aggregation of these measures and the precise definition of latent variables. The measures that will be used are the following:

- Emotional Abuse Questionnaire (EAQ) (Babcock, Jacobson, Gottman, & Yerington, 2000; Jacobson & Gottman, 1998).
- Relationship Satisfaction Scale (Burns, & Sayers, 1992).
- Personal Assessment of Intimacy in Relationships (PAIR) (Schaefer, & Olson, 1981).
- Dyadic Adjustment Scale (DAS) (Spanier, 1976).
- Revised Dyadic Adjustment Scale (RDAS) (Busby, et. al 1995).
- Conflicts & Problem Solving Scale (CPS) (Kerig, 1996).
- Managing Affect and Differences Scale (MADS) (Arellano & Markman, 1995).
- Difficulties in Emotional Regulation Scale (DERS) (Gratz, & Roemer, 2004) will be used to assess affect regulation.
- Experiences in Close Relationships Scale (ECR) (Brennan, Clark, & Shaver, 1998) will be used to assess the attachment in relationships.
- Coping Inventory for Stressful Situations (CISS) (Endler & Parker, 1990) will be used to assess affect regulation.
- Family Daily Hassles Index (FDHI) (Rollins, Garrison, & Pierce, 2002) will be used to measure family stress/hassles and health status.
- Interpersonal Reactivity Index (Davis, 1983) will be used to measure empathy and perspective taking.
- Perceived Stress Scale (PSS10) (Cohen, et al 1983).

Participants can quit the study anytime they would like and there will be no penalty for dropping out of the study. If a participant drops out of the study, the PI will make at least 3 attempts to contact the participant, consisting of phone calls and a certified letter. The participants will be encouraged to perform a final follow-up visit.

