Participants may become distressed due to the sensitivity of the particular topic. There is also a risk of unanticipated change in the participants' relationship. One of the risks of couple's therapy is the end of the relationship or divorce as a possible outcome of the partners gaining insight into the relationship. In clinical trials, attachment based therapies have been shown to be effective in treating couples with negative affect cycles and conflicts (Johnson & Whiffen, 1999), however, there may be a risk of escalation of conflict during the study. Several prevention strategies and safety interventions from the literature will be used to prevent and deal with such situations. Please see Section 16.1 (Data and Safety Monitoring for a detailed plan for maintaining the safety of the participants).

Benefits

The participants may benefit from this study in terms of improved handling of conflict in their relationship.

Alternatives to participation

Alternative treatment options are available in the community to treat IPV. These options include anger management groups for the offenders and self-esteem groups for the survivors of IPV. Also, participants can seek individual and couple therapy as alternative treatment options. Participants will be provided with a list of alternative treatment options during the informed consent procedure so as to avoid undue influence or coercion. Please see the appendices for the list of care providers and local resources.

Principal Investigator: [name]

Protocol Summary for IRB: Feasibility Study of Couple Therapy Treatment for Situational Couple Violence (IRB# 09-13-27)

Withdrawal from Study Participation

Voluntary participation. Participation is completely voluntary, and participants will be encouraged to terminate their participation in the proposed study if they express discomfort. If the couple chooses to withdraw from the study, they will be referred to other therapy and the referral list will be provided.

Both partners need to be willing to attend the therapy. If one partner decides to quit the study, we will stop and referrals will be provided. If one or more of the participants are willing to continue therapy individually, the PI will continue to see them individually until each of them secures a therapist. In that case, data collection with the couple will be discontinued.

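### Break-up is a listed risk, but no named measure records relationship status or contact after baseline, and the rules conflict on whether separated couples are assessed (minor)

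*Combined protocol and SAP*

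**What the plan says.** All references are to the combined protocol and SAP.

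**Break-up is foreseen.** Risks and Benefits (Risks) states that "One of the risks of couple's therapy is the end of the relationship or divorce as a possible outcome". The literature review describes an earlier couples programme that reported this outcome next to violence: "one year after counseling, 78% reported a reduction or cessation of violence with 79% remaining together". The inclusion criteria require that both partners wish to stay in the relationship, but only at entry.

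**What is measured after baseline.** Under Screening Measures, the CTS2 entry says: "This is also be used throughout the study to monitor" (the sentence goes on to change in the relationship). Under Behavioral Measures, at each visit "participants will complete questionnaires measuring attachment patterns, affect regulation, dyadic adjustment, emotional abuse, and IPV". Physiological Measures adds measures of things that may affect cortisol, among them conflict and unusual events, without naming an instrument. Data Monitoring lists demographic and behavioural self-report, cortisol and heart rate as the final dataset.

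**Whether a separated couple is assessed.** Study Design says: "If a couple discontinues after the baseline and before the end of the study (EOS), the EOS assessments should be obtained". Behavioral Measures adds at least three contact attempts for dropouts and encourages a final visit. Withdrawal from Study Participation covers the case where one partner quits and therapy continues individually: "In that case, data collection with the couple will be discontinued". Payments to Subjects makes the session fee conditional on taking part as a couple.

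**Order of assessment.** "The participants will fill out the questionnaires after the collection of physiological data", and for the physiological session "the couple will be reunited and cortisol and vagal reactivity of both partners will be measured following a discussion of a relationship conflict".

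**Analysis.** Aim 2 asks whether violence falls after therapy, using chi-square tests and qualitative analysis. It gives no rule for separated or missing couples.

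**The concern.** The hypothesis is that therapy lowers violence through better affect regulation while the couple stays together. Partners who part have less opportunity for violence, chiefly physical acts, whatever therapy did. Two things can then go wrong in Aim 2:

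- **The couple is lost.** Following the payment rule, the withdrawal rule and the order of assessment would tend to drop it, for a reason related to the outcome.
- **The couple is assessed.** Its lower CTS2 frequency cannot then be separated from reduced contact, because no named item records contact.

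The direction of error is not fixed. Counting lost contact as improvement after therapy favours therapy. Losing a couple that had truly improved works against it, as does counting a couple that parts during Group 2's wait as improved. Contact during a reporting period cannot be fully reconstructed later.

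**Working it through.** **1. The rules side by side**

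| Provision | Effect on a couple that parts |
|---|---|
| Study Design, end-of-study rule | Seeks a final assessment |
| Behavioral Measures, dropout contact | Encourages a final visit |
| Withdrawal from Study Participation | Stops couple data collection if a partner quits and therapy continues individually |
| Payments to Subjects | No fee unless they take part as a couple |
| Physiological and Behavioral Measures | Questionnaires come after a joint task |

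The first three can be partly reconciled as stopping ongoing collection and then seeking one last visit. None covers partners who have parted but would each attend separately, and the last two provisions work against it.

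**2. The plan's own power figure**

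The plan states power .40 for the chi-square test at effect size .60. I read this as w, with 1 df and alpha 0.05 (alpha is not stated). The noncentrality is N × w².

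- N = 8 couples: 8 × 0.36 = 2.88, power 0.396, which matches .40 with the couple as the unit.
- N = 7: 2.52, power 0.355.
- N = 6: 2.16, power 0.312.

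Losing one or two couples lowers a power that is already low by about 4 or 8 points.

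**3. How often a couple might part (illustration only)**

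Study Design gives involvement of 5 months (Group 1) and 7 months (Group 2): 4 × 5 + 4 × 7 = 48 couple-months = 4 couple-years. With a constant yearly probability s of staying together, P(at least one parts) = 1 − s⁴.

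- s = 0.79 (the cited programme): 1 − 0.79⁴ = 61.0%. Expected number: 4(1 − 0.79^(5/12)) + 4(1 − 0.79^(7/12)) = 4(0.0935) + 4(0.1285) = 0.89 couples.
- s = 0.90 (assumed): 34.4%.
- s = 0.95 (assumed): 18.5%.

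**4. What one couple does to a group of four**

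The plan does not define the chi-square categories, so a yes/no improved outcome is assumed. Let k of the other three couples improve.

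| k | Counted improved, (k+1)/4 | Counted not improved, k/4 | Excluded, k/3 |
|---|---|---|---|
| 0 | 25% | 0% | 0% |
| 1 | 50% | 25% | 33.3% |
| 2 | 75% | 50% | 66.7% |
| 3 | 100% | 75% | 100% |

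A wrong score moves the group rate by 25 points up or down. Exclusion moves it by k/12, 0 to +25 points, if the couple had not improved, and by (k − 3)/12, −25 to 0 points, if it had. Over all 8 couples the limits are 12.5 points either way.

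**The case against.** **Staff would often know.** During therapy the therapist meets each partner individually after sessions and calls between them. At each assessment the therapist also works with participants before they leave. One therapist treats all eight couples. This largely stands: what is missing is a recorded status and a measure of contact more than awareness of a break-up. No weekly sessions are described for Group 2's wait or the three months before follow-up, so awareness there is less sure.

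**Lost and misread largely exclude each other.** If the questionnaires really follow the joint task, a separated couple that does not do the task never reaches the CTS2, so no false improvement is scored. This stands, and it is why loss is the likelier outcome. A reader might infer that break-ups would silently be counted as therapy successes. The documents do not support that: loss is more likely, staff would often know, and the direction is uncertain.

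**The absence may only be apparent.** Table 2, Fig 1 and the questionnaire items are not visible. The demographic data or the unusual-events measure might hold relationship status. This stands, so the claim covers named measures only.

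**The safety steps are weak evidence of break-up.** A reader might infer that the protocol itself ends relationships, from Safety Information item 7 and the Safety Chart. Item 7 concerns going home after a session, and the chart may mean only a move to individual sessions.

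**The size is generic.** The 25 points is simply one quarter and applies to any misclassified couple. The plan calls itself a feasibility study and states power of .40. Both are fair, and they keep the point minor.

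**Aim 2 has other checks.** Qualitative analysis and the physiological data could help interpret a fall in violence. They help little for a separated couple, whose reactivity data need the joint task.

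**Conclusion.** The concern holds as a minor point. Break-up is a named risk, no measure named in the readable text records status or contact after baseline, and the assessment rules conflict. As written, a separated couple is most likely lost for a reason tied to outcome. If it is assessed, its CTS2 frequency cannot be read without knowing contact.

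One such couple is a quarter of its group. The 25-point figure rests on an assumed yes/no outcome. The 19% to 61% range rests on assumed yearly separation rates of 5% to 21% and a constant rate. The upper figure comes from a different programme, measured one year after counselling, and its couples may differ from these, who must want to stay together. The documents do not establish a bias in favour of therapy, nor that relationship status is recorded nowhere.

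**What to change.** 1. With each post-baseline CTS2, ask each partner separately for relationship status and for the amount of contact with the partner in the reporting period.
2. Amend Payments to Subjects and Withdrawal from Study Participation. After a separation or one partner's withdrawal, each willing partner should still complete the separate-room questionnaires, paid individually, at every remaining assessment. This must include Group 2's reassessment before therapy, or a couple that parts during the wait can still be lost. Omit the joint conflict task if the couple has parted or either partner feels unsafe.
3. In Aim 2, list separated couples by group and show the result with them included and excluded.

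**Cost.** Two questions, short amendments to the payment, withdrawal and assessment rules, and one display. Payments are at most 2 partners × 2 sessions × $20 = $80 per separated Group 1 couple and 2 × 3 × $20 = $120 per Group 2 couple, which is what they would have received attending as a couple. Those couples would have no cortisol or vagal reactivity data, and the Aim 2 result may look less favourable.

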Appendix: Safety Chart

Prevention

- Exclude high risk couples from the study
- *Identify the risk factors for further violence, including substance abuse, severe mental health problems, having previously violent relationships, access to firearms, and comfort with severe violence. (Please see details for exclusion criteria).*
- *Teach techniques that participants can use at home*
- Timeout procedures, stress management techniques, anger control & problem solving techniques. (Please see handouts for these techniques)
- Provide a referral sheet for the participants with numbers and location of various emergency services as well as 24 hour hotline numbers

During intervention

- *Identify the conflict issues between the couple and discuss situations in which violence may be prompted along with what can be done to avoid or work against such situations.*
- The therapists will meet clients individually after each session to make sure that they feel safe going home with their partners.
- *Monitor possible buildup tension between the partners.* The therapists will see the participants in weekly scheduled sessions and will call the participants at least once in between sessions to monitor the buildup of tension.
- Each partner will also be provided by a phone number at which they can reach the therapist and arrange for individual time with the therapist if they wish to.

Worst Case Scenario

- Follow the emergency protocol
- Therapist will separate the couple and continue to see them as individual clients.
- Make appointment for the next session.
- Participants will be taught of safety planning and handouts will be provided (Please see appendix for the handouts).
- *Provide an emergency contact number for the participants.* The participants will be provided a phone number of an experienced therapist to contact in case of emergencies. This phone number will be associated with a voice mail that is remotely accessible. Participants will also be advised to call 911 in case of emergencies that needs prompt response.
- A referral sheet will be provided to the participants with the information about shelters. The referral sheet will also include numbers and locations of area mental health providers as well as the fee associated with their services. (Please see appendix for the referral sheet).
